2.4. CHANGES TO ANALYSIS FROM PROTOCOL

- Change in definition of efficacy analysis set (EAS), in [section 4.4](#).
- Analysis to be performed based on EAS has been revised to exclude PFS and OS in [section 4.4](#).
- Subsequent oncology therapy was not defined in the protocol. The definition and analysis has been added in [section 13](#) of SAP
- Changes on criteria of Hy's Law; "Serum AST or ALT $\geq 3 \times$ ULN and ALP $< 2x$ ULN and total bilirubin $\geq 2 \times$ ULN" is changed to be "Hy's Law: Serum AST or ALT $> 3 \times$ ULN and ALP $< 2x$ ULN and total bilirubin $> 2 \times$ ULN", in section [17.4.4](#).
- Changes on criteria of drug-induced liver injury (DILI); "Serum AST or ALT $\geq 3 \times$ ULN together with total bilirubin $\geq 2 \times$ ULN" is changed to be "Serum AST or ALT $> 3 \times$ ULN together with total bilirubin $> 2 \times$ ULN", in section [17.4.4](#).

3. PLANNED ANALYSES

The timing of analysis for each cohort may be different depending on completion of each cohort, and the final analysis of the study will be conducted at the time of analysis of the last cohort. No formal interim analysis is planned for the study. However, the accrued data from any cohort may be analyzed for internal decision-making purposes; for example, to provide information for a future trial or external data disclosures. Then, the Database Lock (DBL) authorized by sponsor will be planned depending on the purpose of the analysis.

The final analysis will be planned to be carried out after a DBL. The DBL of final analysis is performed according to the study termination criteria (but not limited to) as below:

- The study is completed when all patients have discontinued study drug or the last enrolled patient have completed 1 year of treatment

OR

- If the study is terminated early for reasons including but not limited to:
 - The incidence or severity of adverse events (AEs) in this or other studies indicates a potential health hazard to patients.
 - Patient enrollment is unsatisfactory.

3.1. INTERIM ANALYSIS

No formal interim analysis is planned for the study. However, the accrued data from any cohort may be analyzed for internal decision-making purposes; for example, to provide information for a future trial or external data disclosures. During the analysis, selected summary for safety and anticancer activity of fruquintinib will be performed.

Document: [REDACTED]

Author: [REDACTED]

Version Number:

2.5

Version Date:

18Feb2022

Template No.: [REDACTED]

Reference: CS_WI_BS005

Effective Date: 02Dec2019

3.2. FINAL ANALYSIS

All final, planned analyses identified in this SAP will be performed by IQVIA Biostatistics following Sponsor Authorization of this Statistical Analysis Plan and Database Lock for this study.

4. ANALYSIS SETS

Agreement and authorization of patients included/excluded from each analysis set will be conducted prior to database lock.

4.1. ALL PATIENTS ENROLLED SET [ENR]

The analysis set contains all patients who provide the informed consent form for this study.

4.2. SAFETY ANALYSIS SET [SAS] – (ALL TREATED POPULATION)

The analysis set includes all patients who have received at least one dose of fruquintinib. Patients in the SAS will be analyzed by their actual dose initially received. If patients have dose reduction during the study, all data will be summarized/analyzed on the initial dose of study drug received.

All safety analyses except for DLT summaries, along with PFS and OS will be based on the SAS.

If there is any doubt whether a patient was treated or not, they will be assumed treated for the purpose of analysis.

4.3. DOSE-LIMITING TOXICITY EVALUABLE SET [DLT]

The analysis set comprises all SAS patients who are evaluable for DLT assessment. DLT evaluable patients are identified if [Yes] is ticked as the response to “DLT Evaluable Patients” on CRF. DLT set and summaries will only apply to dose escalation phase.

4.4. EFFICACY ANALYSIS SET [EAS]

This analysis set includes all patients who have received at least 1 dose of fruquintinib, have a measurable lesion (target lesions ≥ 10 mm) at the baseline tumor assessment, and either (i) have had at least one post-baseline tumor assessment, or (ii) do not have post-dose tumor assessment but have clinical progression as noted by the investigator, or have died due to disease progression before their first post-baseline tumor scan. All efficacy endpoints (i.e. BOR, ORR, DCR, DoR, and best percentage change from baseline in tumor size), not including PFS and OS, will be summarized based on this analysis set.

Document: [REDACTED]

Author: [REDACTED]

Version Number: 2.5

Version Date: 18Feb2022

Template No.: [REDACTED]

Reference: CS_WI_BS005

Effective Date: 02Dec2019

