Efficacy	
All patients from the safety analysis set who have at least one post-baseline tumor assessment will be included in the efficacy analysis set (EAS).
 
The ORR and DCR will be summarized by dose cohort with percentages and 95% exact confidence intervals for the EAS. The PFS rate at specific time points (eg, PFS rate at 12 weeks for Cohort C) and its 95% confidence interval will be estimated using the Kaplan-Meier method. PFS, DoR, and OS will be summarized descriptively using Kaplan-Meier medians and quartiles for patients in the SAS. Percentage change in tumor size will be determined for patients with measurable disease at baseline and will be derived at each visit by the percentage change in the sum of the diameters of target lesions (TLs) compared to baseline. The best percentage change in tumor size will be summarized using descriptive statistics and presented using a waterfall plot.

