## 6.4 Efficacy Assessments

### Tumor Assessment

All measurable and evaluable lesions should be assessed and documented at screening and re-assessed at each subsequent tumor evaluation (see [Appendix A](#)). Assessments should include computed tomography (CT) scans with oral or IV contrast (unless contraindicated) of the chest, abdomen, and pelvis. MRI scans are allowed if CT contrast is contraindicated. Other methods of assessment should be utilized as clinically indicated.

**Tumor assessments for dose escalation cohorts, Dose Expansion Cohort C, Dose Expansion Cohort D, and Dose Expansion Cohort E** are scheduled at Screening and every 8 weeks ( $\pm$ 1 week) thereafter, ie, C3D1, C5D1, C7D1, etc. (odd-numbered cycles).

**Tumor assessments for Dose Expansion Cohort A and Dose Expansion Cohort B** are scheduled at Screening, C2D1, C3D1, C4D1, and every 8 weeks ( $\pm$ 1 week) thereafter, ie, C6D1, C8D1, C10D1, etc. (even-numbered cycles).

Subjects who permanently discontinue study drug for reasons other than progression of disease should continue to be followed for efficacy according to the schedule in [Appendix A](#).

All subjects are to have tumor assessments performed at the Treatment Completion visit, unless the subject was discontinued from treatment because of disease progression or the subject had tumor assessments performed within 14 days of the last dose of study drug.

At the investigator's discretion, CT scans may be repeated at any time if progressive disease is suspected.

Disease status will be assessed using RECIST Version 1.1 (see [Appendix C](#)). The same imaging procedure used to define measurable lesions at baseline must be used throughout the study for each patient.

At the investigator's discretion, other methods of assessment of measurable disease as per RECIST may be used. Examples of other assessment methods include tumor markers, such as prostate-specific antigen (PSA) and cancer antigen 125 (CA-125) levels for patients with prostate and ovarian cancer, respectively. However, tumor markers alone cannot be used to assess response. If markers are initially above the upper normal limit, they must normalize for a patient to be considered in complete response.

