## 6.5 Study Completion/Early Termination Visit

Patients who complete the study or discontinue study drug will be asked to return to the

clinic at 30 ( $\pm$  7) days after the decision to permanently discontinue treatment with fruquintinib. Ongoing AEs will be followed until the event has resolved to baseline grade, the event is assessed as stable by the investigator, new anti-tumor treatment is initiated, the patient is lost to follow-up, the patient withdraws consent, or when it has been determined that the study treatment or participation is not the cause of the AE.

Please see the Study Flowchart provided in [Appendix A](#) for assessments to be performed at the study completion or early termination visit.

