### 8.1 Analysis Populations

The following analysis populations are defined for the study:

- Safety Analysis Set (SAS): This population includes all patients who have received at least one dose of fruquintinib. Safety data will be evaluated based on this population's outcome. Patients in the SAS will be analyzed by their actual dose initially received. If patients have dose reduction during the study, all data will be summarized/analyzed based on the initial dose of study drug received.
- Pharmacokinetic Analysis Set (PKAS): This population will include all patients who received at least one dose of fruquintinib and have at least 1 PK sample obtained and analyzed.
- Efficacy Analysis Set (EAS): This population includes all patients who have received at least 1 dose of fruquintinib and have at least 1 post-baseline tumor assessment. All efficacy endpoints will be analyzed based on this analysis set.

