### Reporting of Results

- All patients included in the study must be assessed for response to treatment, even if there are major protocol treatment deviations or if they are ineligible. Each patient

will be assigned one of the following categories: 1) complete response, 2) partial response, 3) stable disease, 4) progressive disease, 5) early death from malignant disease, 6) early death from toxicity, 7) early death because of other cause, or 9) unknown (not assessable, insufficient data).

- All the patients who met the eligibility criteria should be included in the main analysis of the response rate. Patients in response categories 4-9 should be considered as failing to respond to treatment (disease progression). Thus, an incorrect treatment schedule or drug administration does not result in exclusion from the analysis of the response rate. Precise definitions for categories 4-9 will be protocol specific.
- All conclusions should be based on all eligible patients.
- Subanalyses may then be performed on the basis of a subset of patients, excluding those for whom major protocol deviations have been identified (eg, early death due to other reasons, early discontinuation of treatment, major protocol violations, etc.). However, these subanalyses may not serve as the basis for drawing conclusions concerning treatment efficacy, and the reasons for excluding patients from the analysis should be clearly reported.
- The 95% confidence intervals should be provided.

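### SAP Appendix 3 codes a response after SD as SD in the unconfirmed ORR, and SAP 4.4 drops never-scanned patients from ORR and DCR unless they failed by progression

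*SAP*

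**What the plan says.** **Response set.** SAP 4.4 requires at least one dose, a measurable lesion at baseline, and a post-baseline tumor assessment. It makes one exception to the last requirement, for patients who "do not have post-dose tumor assessment but have clinical progression as noted by the investigator, or have died due to disease progression" before a first scan. BOR, ORR, DCR, DoR and change in tumor size use this set. PFS and OS use all treated patients (SAP 4.2, 4.4).

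Protocol 8.1 defines the set differently: "This population includes all patients who have received at least 1 dose of fruquintinib and have at least 1 post-baseline tumor assessment". The synopsis agrees: "All patients from the safety analysis set who have at least one post-baseline tumor assessment will be included in the efficacy analysis set (EAS"). Neither asks for measurable disease. SAP 2.4 declares the change of definition, and SAP 8.1 tabulates reasons for exclusion from each set.

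**Unconfirmed response.** SAP 16.1.1 adds unconfirmed CR and unconfirmed PR as categories when a confirming scan is absent or too early, and sends the reader to Appendix 3 to derive BOR. Scenario #2 of SAP 16.1.2 counts every response, confirmed or not, and scores any other BOR as No. In the unconfirmed column of Appendix 3:

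| First | Second | Unconfirmed column |
|---|---|---|
| NE | CR | Unconfirmed CR |
| NE | PR | Unconfirmed PR |
| SD | CR | SD |
| SD | PR | SD |

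**The concern.** The two SD rows contradict the rule that they are meant to implement. Nothing in 16.1.1 or 16.1.2 withholds the unconfirmed category because an earlier scan showed SD, and the same table grants it after NE. Two programmers could produce different unconfirmed rates from the same data.

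The response set raises a separate question. Whether a never-scanned patient stays in the denominator depends on why the patient failed. Toxicity, withdrawal of consent and loss to follow-up are all listed as reasons for stopping treatment in protocol 3.6. A patient who leaves by one of these routes before any scan, or dies of a cause other than the tumor, is dropped, while one who progressed is kept. The dropped patients cannot contribute a response, so the effect on ORR and DCR has only one direction. The study tests no hypotheses (SAP 5.5), so these estimates are themselves the result.

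**Working it through.** **1. The plan's own precision figures.** Protocol Tables 15 and 16 give Clopper-Pearson limits: the lower is the 0.025 quantile of Beta(x, n−x+1), the upper the 0.975 quantile of Beta(x+1, n−x). For 4/40 this gives 0.028 to 0.237 (table: 0.03, 0.24). For 3/15 it gives 0.043 to 0.481 (table: 0.04, 0.48). All twelve rows match to two decimals.

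**2. Appendix 3 against SAP 16.1.2.** The table has 21 rows, of which 14 contain a CR or PR. Twelve of these 14 count as a response in the unconfirmed column. The two that do not are SD-then-CR and SD-then-PR. The seven rows without a CR or PR are correctly non-responses.

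Each patient lost this way costs 1/n:
- n=40: 1/40 = 2.5 points, for example 4/40 = 10.0% in place of 5/40 = 12.5%.
- n=15: 1/15 = 6.7 points, for example 3/15 = 20.0% in place of 4/15 = 26.7%.

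The number of such patients is an assumption; the documents give none.

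**3. How the two-column table handles longer sequences.** Take SD, then PR, then no further scan.
- *First two time points only:* the SD-PR row gives SD, and the response is lost.
- *Successive pairs:* SD-PR gives SD, but PR followed by NE or NA gives Unconfirmed PR, so the response is recovered and the loss is zero.

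The first reading would also code SD-PR-PR, a confirmed late response, as SD in the confirmed column. SAP 16.1.1 uses time-point responses up to the last evaluable one, and footnote ^ of Appendix 3 discusses runs of three and four scans. Both imply longer sequences, but neither states how to apply the table to them.

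**4. The denominator.** Let n be the treated patients with measurable disease, x those with the outcome, and k those never scanned for a reason other than progression. Counting the k as NE gives x/n; SAP 4.4 gives x/(n−k). The ratio is n/(n−k), which is never below 1.

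The values of k and x below are illustrative. The same range of k is used for both sizes, because the documents support no difference by cohort. The planned sizes of 40 and 15 are treated as if every patient had measurable disease.

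| k | DCR, x=20, n=40 | ORR, x=4, n=40 | DCR, x=6, n=15 |
|---|---|---|---|
| 0 | 50.0% (33.8–66.2) | 10.0% (2.8–23.7) | 40.0% (16.3–67.7) |
| 1 | 51.3% (34.8–67.6) | 10.3% (2.9–24.2) | 42.9% (17.7–71.1) |
| 2 | 52.6% (35.8–69.0) | 10.5% (2.9–24.8) | 46.2% (19.2–74.9) |
| 4 | 55.6% (38.1–72.1) | 11.1% (3.1–26.1) | 54.5% (23.4–83.3) |

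Every shifted estimate lies inside the interval for k=0.

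**5. What limits k.** Under protocol 6.4, patients who stop "for reasons other than progression of disease should continue to be followed for efficacy". The same section adds: "All subjects are to have tumor assessments performed at the Treatment Completion visit, unless the subject was discontinued from treatment because of disease progression" (or a scan is recent enough). Protocol 6.5 places that visit 30 (±7) "days after the decision to permanently discontinue treatment with fruquintinib". Only a patient who misses both the scheduled scans and the completion scan is dropped.

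**The case against.** A response-evaluable set is a recognised choice in an open-label Phase 1/1b study, SAP 2.4 declares it, and ORR and DCR are secondary and descriptive. The add-back also has a logic: progressors are excused the completion scan, so they are the patients most likely to have none. Exclusions and reasons are tabulated, so a reader can largely rebuild the fuller denominator. Scoring an unscanned withdrawal as a failure is itself a convention, since the true disease status is unknown. All of this stands, and it argues against replacing the main set. It does not argue against showing the fuller denominator once.

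On Appendix 3, the fair reply is that successive pairs must be intended, because the literal reading gives an absurd result for SD-PR-PR. That is persuasive about intent, but the rule is unwritten and the two cells still say SD.

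A reader might infer that SAP 4.4 breaks a binding rule in protocol Appendix C, which says: "Patients in response categories 4-9 should be considered as failing to respond to treatment (disease progression"). The documents do not support that. Appendix C is RECIST reference text, and it adds: "Precise definitions for categories 4-9 will be protocol specific".

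A reader might also try to state how much closer SAP 4.4 comes than protocol 8.1 to an all-treated rate. The SAP adds back some never-scanned patients but also removes scanned patients with bone-only disease, whom inclusion criterion 7 admits. Any such share would have to assume that there are none.

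**Conclusion.** The two SD cells in the unconfirmed column are wrong as written and should be corrected. The loss is 2.5 points per affected patient at n=40 and 6.7 at n=15 if the rows are applied directly, and possibly zero under successive pairs. It falls on the supportive unconfirmed ORR. The confirmed ORR would be touched only under the literal two-time-point reading, which the SAP's own wording makes unlikely.

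The SAP 4.4 rule is a declared choice with a known direction: against all treated patients with measurable disease, it can only raise ORR and DCR or leave them unchanged. Its size is unknown and probably small; the tabulated shifts rest on assumed counts. A first scan at week 8 (dose escalation, Cohorts C, D and E) leaves a longer unscanned period than one at C2D1 (Cohorts A and B), but the documents give no basis for numerical ranges that differ by cohort. They also do not support the inference that the primary endpoint is biased: PFS, like OS, is analysed on all treated patients and is unaffected by either point.

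**What to change.** 1. **SAP Appendix 3, unconfirmed column.** Change SD-then-CR to Unconfirmed CR and SD-then-PR to Unconfirmed PR. Add one sentence saying that the table is applied across all time points up to the last evaluable one, so that a response after SD can be confirmed by a later scan. Cost: two cells and a sentence.
2. **SAP 16.2.** Keep the declared EAS as the main set. Add one supportive ORR and DCR table on all treated patients with measurable disease at baseline, counting those with no post-baseline scan for any reason as NE, a category that SAP 16.1.1 already has. Say that bone-only patients remain outside it. Cost: one extra table, with supportive rates that may be slightly lower. No protocol amendment is needed.

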5. GENERAL CONSIDERATIONS

5.1. REFERENCE START DATE AND STUDY DAY

Reference start date is defined as the day of the first dose of study medication. Study Day will be calculated from the reference start date and will be used to show start/ stop day of assessments and events. Study day will appear in every listing where an assessment date or event date appears.

If the date of the event is on or after the reference date then:

$$\text{Study Day} = (\text{date of event} - \text{reference date}) + 1.$$

If the date of the event is prior to the reference date then:

$$\text{Study Day} = (\text{date of event} - \text{reference date}).$$

In the situation where the event date is partial or missing, the date will appear partial or missing in the listings, but Study Day and any corresponding durations will be presented based on the imputations specified in [section 6.3](#).

5.2. BASELINE

Unless otherwise specified, baseline is defined as the last non-missing measurement taken prior to reference start date (including unscheduled assessments). In the case where the last non-missing measurement and the reference start date coincide, that measurement will be considered baseline, unless additional information collected on eCRF indicate otherwise.

For example, ECG will be considered being performed post-baseline if assessment date coincides with the reference start date but “Time Point” on “ECG (ECG)” form indicates the assessment was performed “Post-dose 3 hours (\pm 15 minutes)”. Adverse Events (AEs) onset on the reference start date and with “Did the adverse event occur prior to the start of study treatment?” in “Adverse Events (AE)” form answered as “No” or not being answered will be considered as post-baseline. Medications commencing the reference start date will be considered post-baseline.

5.3. UNSCHEDULED VISITS AND EARLY TERMINATION DATA

In general, for by-visit summaries, data recorded at the nominal visit will be presented. Unscheduled measurements will not be included in by-visit summaries, but will contribute to the best/ worst case value where required (e.g., shift table).

Listings will include scheduled, unscheduled, and early discontinuation data.

Document: [REDACTED]

Author: [REDACTED]

Version Number:

2.5

Version Date:

18Feb2022

Template No.: [REDACTED]

Reference: CS_WI_BS005

Effective Date: 02Dec2019

5.4. WINDOWING CONVENTIONS

The visit-window mapping is described in [APPENDIX 4](#). Visit-based summaries will be based on the windowed visits. All data, whether or not within the visit windows, will be presented in listings.

For windowed visits during the treatment cycles,

- If more than 1 assessment occurs during a visit window, the assessment closest to the scheduled day will be assigned to the windowed visit.
- If two assessments are equidistant from the scheduled day, the later assessment will be assigned to the windowed visit.
- If there are multiple assessments on the same day, the worst case will be used.

For the post-treatment visit, the last assessment in the window will be included in the summary. The window for the post-treatment visit will be "from the last dose date + 8 days to the last dose date + 37 days".

For a patient who prematurely discontinues the study, the premature visit will be slotted accordingly.

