**Table 8 Dose Modification for Hematologic and Non-Hematologic Toxicity**

NCI CTCAE v4.03 Toxicity Grading	Action
Grade 1 or 2 a	None
Grade 3 b	Interrupt the dose until the toxicity resolved to ≤Grade 1 or baseline level within 14 days, then reduce the dose to lower a dose level
Grade 4	Discontinue treatment permanently

a Should any arterial thrombosis occur, the treatment should be terminated.

b Including Grade 3 diarrhea and stomatitis, etc. that are ineffectively treated by drug therapies, but excluding Grade 3 menstrual cycle extension.

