17.4.2. CTCAE GRADING FOR LABORATORY DATA

To identify laboratory values of potential clinical importance, laboratory results will be graded according to NCI CTCAE Ver. 4.03, where applicable ([APPENDIX 6](#)). All grading will be based on laboratory values (being direct or some derived, corrected values) only, regardless of its interventional or symptomatic consequences.

Some modifications to the grading system will be applied:

- Grade 5 refers to fatal outcomes, which cannot be determined solely by laboratory values, therefore will not appear in the grading system.
- A further category denoted Grade 0 would include all laboratory values within normal range except missing values.
- Missing results shall be graded as missing.
- For some specific parameters with CTCAE grading in both high and low direction (e.g., calcium, glucose, magnesium, potassium, sodium), CTCAE in hyper and hypo directions will be presented separately, i.e., hyper for higher values of concern and hypo for lower values of concern.

Any graded abnormality that occurs following the initiation of study drug and represents at least a 1-grade change (i.e. increase or decrease) from the baseline assessment is defined as treatment emergent. The treatment-emergent laboratory abnormality defined by CTCAE will be summarized by CTCAE term, CTCAE toxicity grade, and visit. Any occurrence of grade 3 or grade 4 laboratory abnormality during the treatment period will also be summarized by visit.

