APPENDIX 4. VISIT-WINDOW MAPPING

Document:	[REDACTED]	Version Number:	2.5
Author:	[REDACTED]	Version Date:	18Feb2022
Template No.:	[REDACTED]	Reference:	CS_WI_BS005

Effective Date: 02Dec2019

	Cycle 1				Cycle 2-3		Cycle 4 and onwards	Post-treatment
Visit	C1D1	C1D8	C1D15	C1D22	CxD1	CxD15	CxD1	
Scheduled Day [a]	1	8	15	22	1	15	1	
ECOG	Day 1		2 to EOC-3		Day -3 to 3	4 to EOC-3	Day -3 to 3	Last dose date of last cycle +8 to last dose date +37
Vital Sign	Day 1	2 to 11	12 to 18	19 to EOC-3	Day -3 to 3	4 to EOC-3	Day -3 to 3	
Hematology		1 to 11	12 to 18	19 to EOC-3	Day -3 to 3	4 to EOC-3	Day -3 to 3	
Coagulation		1 to 11	12 to 18	19 to EOC-3	Day -3 to 3	4 to EOC-3	Day -3 to 3	
Clinical Chemistry		1 to 11	12 to 18	19 to EOC-3	Day -3 to 3	4 to EOC-3	Day -3 to 3	
Urinalysis		1 to 11	12 to 18	19 to EOC-3	Day -3 to 3	4 to EOC-3	Day -3 to 3	
Thyroid function		1 to 11	12 to 18	19 to EOC-3	Day -3 to 3	4 to EOC-3	Day -3 to 3	
12-Led ECG	Day 1		2 to EOC-3		Day -3 to 3		Day -3 to 3	

[a] The scheduled day is relative to the Day 1 of each cycle.

Note: The end date of a cycle (EOC) is defined as the one day earlier than the date of Day 1 study drug administration of its next cycle. For the last cycle (where no subsequent cycle is given), the end of cycle will be defined as Day 7 relative to the last dose of the cycle.

Tumor Assessment

	Cycle 2	Cycle 3	Cycle 4	8 Weeks after D1 of Cycle 4	8 * (X + 1) Weeks after D1 of Cycle 4 [b]	Post-treatment
Visit	C2D1	C3D1	C4D1	8 Weeks after D1 of Cycle 4	8 * (X + 1) Weeks after D1 of Cycle 4 [b]	
Scheduled Day [a]	1	1	1	57	1 + 7*8 * (X + 1)	
Tumor Assessment (Cohort A and B)	-3 to (EOC-3)	-3 to (EOC-3)	-3 to (EOC-3)	End of Cycle 4 to 85	28 * (2X + 1) + 2 to 28 * (2X + 3) + 1 [d]	Last dose date of last cycle +8 to last dose date +37
	Week 8	Week 8 * (X + 1)				
Visit	Week 8	Week 8 * (X + 1) [b]				
Scheduled Day [c]	57	1 + 7*8 * (X + 1)				
Tumor Assessment (Cohort C, D, and E)	Day 2 to 85	28 * (2X + 1) + 2 to 28 * (2X + 3) + 1 [d]				

[a] The scheduled day is relative to the Day 1 for Cycle 2 to Cycle 4, but the subsequent scheduled day is relative to Day 1 of Cycle 4.

[b] X is an intergerrn starting from 1, and will take maximum value at date of last study drug administration.

[c] Scheduled day is relative to Day 1 of Cycle 1.

[d] The last windowed visit end by the last dose date.

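### SAP 5.3 and 5.4 give conflicting rules for by-visit tables, and under 5.4 a scheduled cycle-start laboratory test followed by a 4- to 14-day dose hold loses its visit

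*SAP*

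**What the plan says.** Two adjacent SAP sections describe how a value is chosen for a by-visit table.

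- Section 5.3: "In general, for by-visit summaries, data recorded at the nominal visit will be presented". It continues: "Unscheduled measurements will not be included in by-visit summaries, but will contribute to the best/ worst case value where required".
- Section 5.4: "Visit-based summaries will be based on the windowed visits". When a window holds more than one test, "the assessment closest to the scheduled day will be assigned to the windowed visit". On ties: "If two assessments are equidistant from the scheduled day, the later assessment will be assigned to the windowed visit". Nothing in 5.4 bars an unscheduled test from filling a window.

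Appendix 4 counts scheduled days from Day 1 of each cycle. The end of a cycle (EOC) is "defined as the one day earlier than the date of Day 1 study drug administration of its next cycle". For haematology, coagulation, chemistry and urinalysis, the Day 1 window from Cycle 2 on is Day -3 to 3. Cycle 1 has a last window for Day 22 (Day 19 to EOC-3). Cycles 2 and 3 have a Day 15 window (Day 4 to EOC-3). From Cycle 4 on, the Day 1 window is the only on-treatment one.

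The outputs concerned are observed values and changes from baseline by visit (SAP 17.4) and the grade tables in SAP 17.4.2: "The treatment-emergent laboratory abnormality defined by CTCAE will be summarized by CTCAE term, CTCAE toxicity grade, and visit". That section also plans a by-visit summary of any Grade 3 or 4 laboratory abnormality on treatment.

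**The concern.** The two rules differ most when a laboratory toxicity delays a cycle. Protocol 5.2.1 allows interruptions of up to 14 days, and Protocol Table 8 describes a hold until recovery to Grade 1 "or baseline level within 14 days, then reduce the dose". Because Appendix 4 ties the cycle boundary to the actual dose, delaying the dose moves the window away from the test that led to the delay. Tests near the restart move into the window instead, and by then the patient has recovered enough to be dosed again. Such tests will often exist: Protocol Table 12 asks for blood counts every 2 to 3 days during a Grade 2 or 3 platelet reduction, and Table 14 asks for more frequent liver tests.

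At stake is whether the by-visit laboratory tables are complete and free of selection on recovery, and whether two programmers working from the same SAP would produce the same tables.

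**Working it through.** No sample size or error rate is involved. The check places one test in the Appendix 4 windows.

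**Inputs and assumptions**

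- A 28-day cycle (Protocol 5.1.6), so the next Day 1 is planned for day 29.
- The scheduled cycle-start test is done on day 29, and dosing is then held for *h* = 0 to 14 days and restarted.
- There is no Day 0 (SAP 5.1).
- Earlier visits took place on time.

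**Formulas**

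- Actual next Day 1 = 29 + *h*. EOC of the previous cycle = 28 + *h*, so EOC-3 = 25 + *h*.
- For *h* of 1 or more, the day of the test relative to the new Day 1 is 29 - (29 + *h*) = -*h*.
- The test is inside the CxD1 window for *h* = 0 to 3 and outside it for *h* = 4 to 14. At *h* = 4, EOC-3 = 29, which is exactly where the previous cycle's last window begins to include it.

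**Result for holds of 4 to 14 days**

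| Held cycle | Window that takes the test | Days from that window's target | Outcome |
|---|---|---|---|
| 2 | C1D22 (day 19 to 25 + *h*) | 29 - 22 = 7 | Loses to an on-time Day 22 test (distance 0) |
| 3 or 4 | Previous cycle's Day 15 (day 4 to 25 + *h*) | 29 - 15 = 14 | Loses to an on-time Day 15 test (distance 0) |
| 5 or later | None | n/a | In no windowed visit |

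If the on-time Day 22 or Day 15 test is missing, the pre-hold value is reported under the wrong visit instead.

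**Shorter holds.** For *h* = 1 to 3 the test stays in the window at distance *h*, but a repeat on the restart day has distance 0 and replaces it. If the test was done *e* days before the planned day, it is outside the window once *h* + *e* reaches 4.

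**Coverage from Cycle 4.** In an undelayed 28-day cycle the Day 1 windows cover days 1 to 3 and the last three days, 6 in all. Days 4 to 25 belong to no laboratory window: 22 of 28, or 79%.

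**Mid-cycle tests.** Tests at C1D8, C1D15, C1D22 and Day 15 of Cycles 2 and 3 that lead to a hold keep their windows, because that cycle's Day 1 is already fixed.

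**Under 5.3.** If the site recorded the day-29 test as the CxD1 visit, it stays at CxD1 for every *h* from 0 to 14.

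**The case against.** The strongest objection concerns the last step above. No passage says that a test taken before a delayed cycle start keeps the CxD1 label. Protocol Appendix A places the visit on Day 1 of the cycle, within 3 days. A site could record CxD1 at the actual restart and the earlier test as unscheduled. Section 5.3 would then exclude it too, and both rules would drop it. This stands: the contrast between 5.3 and 5.4 depends on labelling that the documents do not settle. It does not rescue the by-visit tables, since the pre-hold value is then missing under either rule.

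Second, other outputs keep the value. Protocol 7.1.8.4 requires a laboratory change from baseline that alters study treatment to be reported as an adverse event. It therefore reaches the Grade 3 or higher table (SAP 17.2.1.1) when graded so, and the dose-interruption table (SAP 17.2.2). Worst post-baseline shift tables use scheduled and unscheduled tests (SAP 17.4), listings hold all data (SAP 5.4), and no hypotheses are tested (SAP 5.5). This also stands and limits the harm.

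Third, anchoring on the actual dose is a legitimate convention, and the opening words of 5.3 mark it as a default. Both are fair, but 5.3 does not say when 5.4 overrides it, and the convention leaves a coverage gap from Cycle 4 on.

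Stronger readings are tempting, but the documents do not support them:

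- A reader might infer that any scheduled test leading to a hold is lost. Mid-cycle tests are not.
- A reader might infer that all Grade 3 values disappear from cycle-start rows. Not every Grade 3 value leads to a hold: Protocol 5.2.1 requires none for non-haemolytic anaemia without serious haemorrhage, and Table 14 leaves interruption optional for liver tests short of the Hy's Law criteria. Table 8 is also not the basis for platelets, which Protocol 5.2.2.1 sends to Table 12.
- A reader might want a rate of missed events. The documents give no number of cycle-start holds, so any such figure would be invented.

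**Conclusion.** The concern holds in a limited form. SAP 5.3 and 5.4 give different selection rules for the same tables, and neither is given precedence. Under 5.4 with Appendix 4, a scheduled Day 1 test of Cycle 2 or later followed by a hold of 4 to 14 days leaves the CxD1 window. When the held cycle is Cycle 5 or later it has no windowed visit at all, although SAP 17.4.2 plans to summarise any Grade 3 or 4 occurrence by visit. The by-visit tables can then be incomplete and look milder than what was observed.

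The effect is confined to descriptive by-visit outputs, and its frequency cannot be computed. The placement rests on 28-day cycles, testing on the planned day, on-time earlier visits and a restart of dosing. It does not show that the trial's overall safety reporting hides these events.

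**What to change.** In the SAP:

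1. State one governing rule for by-visit summaries in 5.3 and 5.4.
2. Say whether an unscheduled test may fill a window.
3. State that a scheduled cycle-start test keeps its CxD1 label when dosing is delayed, or anchor the CxD1 window on the planned visit date. List the pre-restart test separately.
4. In Appendix 4, add coverage from Day 4 to EOC-3 for Cycle 4 onward, so that every on-treatment Grade 3 or 4 value is counted in the by-visit table. No visit is scheduled in that interval, so also say which value represents it; the worst grade would serve the grade tables.

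The cost is wording in 5.3, 5.4 and Appendix 4, a small programming change, and a check of how sites labelled tests before a delayed cycle. No new data are needed, and no dosing rule changes.
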